APPENDIX D - STUDY KIT CLEANING INSTRUCTION

Study sensors are reusable after completion of study procedures and data collection. Used study kit containers will be wiped on the outside using Sani-Cloth before handling and placed in a fume hood labeled “Contaminated Study Kits” in accordance with the study protocol.

The following procedures will be conducted by a research assistant from the study sites:

1. The researcher assistant is to wear appropriate PPE including lab coat, and nitrile gloves before handling any study supplies.
2. The fume hood labeled “Contaminated Study Kits” will have all surfaces cleaned and wiped down with Sani-Cloth and/or 70% EtOH solution.
3. The outside of study kit containers will be cleaned and wiped down with Sani-Cloth and/or 70% ETOH solution.
4. Once all used study kits are cleaned on the outside they may be opened, one at a time, to have contents cleaned. All study sensors, devices, chargers, cords and accessories will be wiped with Sani-Cloth and allowed 2 minutes to air dry on a cleaned surface.
5. Sensors will be closely examined for physical breaks, holes or tears in the silicone packaging. Any sensors that have physical damage will be sealed in separate plastic containers or plastic bags and labeled for return to the manufacturer.
6. Do not reuse towelette. Dispose of used Sani-Cloth in trash.
7. Individually wrapped, sealed adhesives may be cleaned in the same process.
8. Unsealed adhesives will be discarded along with any printed materials from the study kit.
9. Once all contents of the study kit have been removed from the container, inside of study kit containers will be cleaned and wiped down with Sani-Cloth and/or 70% EtOH solution. Allow to air dry for 2 minutes.
10. Return study kit contents to the study container.
11. The fume hood with Contaminated Study Kits will have all surfaces cleaned and wiped down with Sani-Cloth and/or 70% EtOH solution.
12. Cleaned study kits may be placed in the “Clean Kits” designated area for reuse.

| Materials and PPE | Study supply kit list |
|---|--|
| 
 ● 70% ETOH ● Super Sani-Cloth Germicidal Wipe* | 
 ● Cardboard mailer box. ● Wearable study sensors ● Study devices (Tablet(s) or smart |

STU#: STU00214445

| | |
|---|---|
| 
• Disposable paper towel• Nitrile Gloves• Lab coat• Face mask* | 
phone(s) with sensor application).
 
• Wireless charger(s), charger cords, bricks• Device accessories; adhesives for both sensors• Printed instructions or study other study materials |
|---|---|

*Super Sani-Cloth is an EPA registered hospital-grade disinfectant to accommodate the many situations and hard non-porous environmental surfaces found in healthcare settings. This wipe kills bacteria, viruses, and yeast.

* Hospital COVID precautions will be used at all times during the study. .

The study sponsor should perform an inspection of each device and ensure cleaning procedures should be conducted before shipping and after receiving the return shipment per guidance from the Center for Disease Control⁸.

STU#: STU00214445

APPENDIX E - STOP-BANG QUESTIONNAIRE

Snoring: Do you snore? Loud enough to be heard through closed doors or loud enough to disturb your partner?

| | |
|------------|-----------|
| Yes | No |
|------------|-----------|

Tired: Do you often feel tired, fatigued or sleepy during the daytime?

| | |
|------------|-----------|
| Yes | No |
|------------|-----------|

Observed: Has anyone observed you stop breathing, choking or gasping while you were sleeping?

| | |
|------------|-----------|
| Yes | No |
|------------|-----------|

Pressure: Are you being treated for high blood pressure?

| | |
|------------|-----------|
| Yes | No |
|------------|-----------|

Body Mass: What is your Body Mass Index (BMI)?

Height (in inches):

Weight (in pounds):

| | |
|------------------------|------------------------|
| Less than 25 | Greater than 25 |
| Greater than 30 | Greater than 35 |

STU#: STU00214445

Age: Are you older than 50?

| | |
|------------|-----------|
| Yes | No |
|------------|-----------|

Is your shirt collar 16 inches / 40 cm or larger?

| | | |
|------------|-----------|----------------|
| Yes | No | Unknown |
|------------|-----------|----------------|

Gender: Are you male?

| | |
|------------|-----------|
| Yes | No |
|------------|-----------|

OSA - Low Risk: Yes to 0 - 2 questions

OSA - Intermediate Risk: Yes to 3 - 4 questions

OSA - High Risk: Yes to 5 - 8 questions

or Yes to 2 or more of 4 STOP questions + male gender

or Yes to 2 or more of 4 STOP questions + BMI > 35kg/m²

or Yes to 2 or more of 4 STOP questions + neck circumference 17 inches / 43cm in male or 16 inches / 41cm in female

STU#: STU00214445

APPENDIX F: Eligibility Screening Questions:

Do you have significant cardiorespiratory disease including any of the following:

Chronic obstructive pulmonary disease (COPD)

Congestive Heart Failure

Atrial Fibrillation

Other (please describe)

Have you previously been hospitalized for cardiorespiratory issues?

-If yes, please describe.

Do you have an implanted pacemaker or defibrillator?

Do you use oxygen while sleeping?

Do you have respiratory muscle weakness due to neuromuscular condition?

Have you experienced awake hypoventilation or suspicion of sleep related hypoventilation (breathing at an abnormally slow rate)?

Have you used opioid medication for more than 3 months?

Have you ever had a stroke?

Do you have a history of severe insomnia?

Do you have a history of dementia?

Follow up enrollment questions:

[figure not shown]
What is the best phone number to reach you at?

What is your preferred email address?

What is the best time to contact you? (Day(s), time(s))

STU#: STU00214445

2.1 Indication for use of ANNE™ Sleep

ANNE Sleep is a wearable sensor system intended for use in the collection, analysis, display, and storage of physiological parameters to aid in the evaluation of sleep-related breathing disorders of adult patients suspected of sleep apnea. The device is intended for use in the clinical and home setting under the direction of a Healthcare Professional (HCP).

2.2 ANNE Sensors Description

ANNE Sleep uses the ANNE Chest and ANNE Limb sensors to detect sleep distorted breathing. The sensors are worn by the patient during a night of sleep. Both sensors wirelessly measure biosignals and transfer them to the ANNE Sleep mobile application through Bluetooth.

The ANNE Chest sensor is placed under the suprasternal notch as shown below (Figure 1) with a silicone gel adhesive. The ANNE Chest measures snoring through the accelerometer z-axis sampled at a high-frequency and chest movement through the x and y-axis.

STU#: STU00214445

[figure not shown]

Figure 1: Placement of the ANNE Chest Sensor

The ANNE Limb sensor is worn on the finger and collects photoplethysmograph (PPG) signals for the calculation of SpO₂, PAT, and pulse rate. The ANNE Limb Sensor is secured to the finger with a medical foam tape adhesive as shown below in Figure 2.

STU#: STU00214445

Figure 2: Limb Sensor worn

2.3 Signals Acquired by ANNE Sleep

The signals listed in Table 1 are used by ANNE Sleep to detect respiratory events. The signals will be available in the EDF file that is generated as part of the data flow. The signals are downsampled to be easily transmitted and viewed.

Table 1: Sleep Signal Generated from the ANNE Sensors

| Signal | Device | Description | Sampling Rate (Hz) |
|-----------------------|--------|---|--------------------|
| PAT (A.U) | Limb | Peripheral Arterial tone | 32 |
| Pulse Amplitude (A.U) | Limb | Pulse amplitude from the PAT signal | 2 |
| Accel Vertical (g) | Chest | Chest movement picked up by ANNE Chest's vertical roll. Refer to Figure 3 | 32 |
| Accel Horizontal (g) | Chest | Chest movement picked up by ANNE Chest's horizontal roll. Refer to Figure 3 | 32 |

STU#: STU00214445

| | | | |
|------------------|-------|---|-----|
| Snore (g) | Chest | Snore signal from ANNE Chest | 256 |
| Pulse Rate (bpm) | Limb | Pulse rate derived from ANNE Limb Sensor | 2 |
| SpO2 (%) | Limb | Oxygen saturation derived from ANNE Limb Sensor | 2 |
| Body Position | Chest | Position of the Body | 1 |

The ANNE Chest Sensor derives horizontal roll and vertical roll from the 3-axis accelerometer to measure the tilt of the sensor in both directions. Displaying the roll of the sensor instead of the acceleration allows the chest movements to be more clearly shown graphically.

[figure not shown]

Figure 3: Accelerometer axis orientation of ANNE Chest

The body position of the patient is also derived by the 3-axis accelerometer. The system provides 5 body positions - upright, supine, prone, left, and right.

3.0 Scoring Procedure

3.1 Data Flow Overview

The high-level data flow is shown below (Figure 4). After the patient has received the ANNE Sleep system and successfully finished their sleep night data collection, the data is downloaded from the sensors and automatically uploaded to the ANNE Sleep Hub. In the ANNE Sleep Hub, the data collected from the ANNE sensors are processed and converted into an EDF format file so that it can be consumed by EDF viewers and scoring platforms such as EnsoSleep. After the dataset has been scored, the scored data is transferred back to the ANNE Sleep Hub for sleep report generation. The report generated can then be reviewed by a Healthcare Professional (HCP) to aid in the evaluation of sleep-related breathing disorders.

STU#: STU00214445

[figure not shown]

Figure 4: ANNE Sleep Data Flowchart

pAHI (peripheral arterial tonometry AHI) is calculated by counting the number of sleep-disordered breathing events for the patient divided by the TST (total sleep time). TST is automatically calculated in ANNE Sleep Hub using pulse rate.

$$pAHI = \frac{\text{Total Number of Disordered Breathing Events}}{\text{Total Sleep Time (hrs)}}$$

3.2 EnsoSleep

The ANNE Sleep system uses EDF viewers or scoring platforms such as EnsoSleep for scoring the sleep recordings. This section contains the steps for scoring ANNE Sleep data with EnsoSleep.

3.1.1 Choosing a patient to Score

Select the dataset to score by identifying them through the Patient column. After selecting the patient, click the vital icon as shown below in Figure 5 to proceed to create a score set.

Updated: 2021/12/02, 8:23 AM ↻ 🔍 ☰ 1-25 of 234 < >

|  | Status | Created | Patient | Study | Desat | |
|--------------------------|----------|--------------------------------------|---------|------------|--------------------------------|---|
|  | Scorer 1 | 2021/11/30 Last Monday 6:26 PM | 511-035 | HST EDF | 3%  4% | ⋮ |
|  | Scorer 1 | 2021/11/30 Last Monday 6:26 PM | 148K | HST EDF | 3%  4% | ⋮ |
|  | Scorer 1 | 2021/11/30 Last Monday 6:26 PM | 193K | HST EDF | 3%  4% | ⋮ |
|  | Scorer 1 | 2021/11/30 Last Monday 6:26 PM | 109K | HST EDF | 3%  4% | ⋮ |
|  | Scorer 1 | 2021/11/30 Last Monday 6:26 PM | 080K | HST EDF | 3%  4% | ⋮ |

Figure 5: EnsoSleep Dashboard

STU#: STU00214445

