4.1 Primary Outcome Measures

- Analysis of variation between nights of AHI derived from ANNE Sleep system across multiple sleep nights at home
- Analysis of agreement for diagnosis of moderate to severe OSA by determining a patient's Apnea-Hypopnea Index (AHI) wearing the ANNE Sleep system and WatchPAT ONE over one (1) night worn concurrently
- Patient responses on psychometric surveys for comfort and usability comparing ANNE Sleep and WatchPAT ONE

•

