8.1.2 Initial Visit Day: Screening/Enrollment

The subject will have the option to discuss with the study coordinator over the phone or by a Zoom teleconference from the subject's personal device. If Zoom communication is selected a unique meeting number and password known only to the subject will be provided. The study coordinator will monitor the number of attendees in the meeting and restrict meetings to IRB approved researchers on this study, the study subject, and additional people at the subject's discretion. Researchers will host the Zoom sessions and will utilize the waiting room feature to ensure that only the appropriate participants are included on the call.

The study coordinator will cover following topics associated with the study during the Screening/Enrollment visit:

STU#: STU00214445

- (1) Informed Consent will be reviewed and signed electronically using REDCap.
- (2) The qualified subject will be asked to schedule a study date to participate at home. The nights of sensor wear do not need to be consecutive. Subjects will be instructed to set-up both devices on Night One of sleep testing and then only the ANNE device on Nights 2-4.
One Night = HST and ANNE Sleep
3 Additional Nights = ANNE Sleep only
The target time frame will be to complete the sleep nights within 8 weeks of enrollment.
- (3) Subjects will be advised to avoid alcohol and sleep medication use such as antihistamine (OTC) or prescribed medicines for sleep support on the testing night. Any use of these substances on the night of monitoring sleep will be asked to be recorded in the diary.
- (4) Subjects will be informed how to complete the Demographic, Medical History and Sleep Survey sleep diary and usability survey (**Appendix A-C**). The surveys should be available to complete via an email link through REDCap or printed out forms.

Any subject's questions or concerns associated with the study will also be addressed.

At least 24 hours prior to the subject's sleep nights, the study coordinator will contact the participant by phone to confirm their planned sleep study nights at home.

The below sections describe the procedures for setting up the ANNE and HST devices, respectively.

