8.1.3 ANNE™ Sleep procedures

The ANNE™ Sleep sensors will be applied by the study subjects themselves.

- 1) The PI or study coordinator will ensure the ANNE™ Sleep sensors are functional and collecting data properly prior to providing to subjects. The study coordinator will provide instructions for use of the ANNE™ Sleep system in the subject study kit.
- 2) Sensor placement (to be completed by the subject):
 - a) Using IPA alcohol wipes, the subject will wipe down the areas of the skin where the sensors will be placed thoroughly to remove any dirt, oils, etc. IPA alcohol wipes will also be used to clean the surface of the sensors before placement. If necessary, the subject may need to shave their chest to provide better adhesion and comfort of the sensor.
 - b) The subject will apply a single use adhesive to the chest sensor and place it on their chest at the suprasternal notch (see Figure 2). The subject will

STU#: STU00214445

attach the limb sensor to their finger using a single-use adhesive (see Figure 2).

[figure not shown]

Figure 2. Placement of the ANNE™ chest and limb sensors

3) Setting up a mobile device with an ANNE Sleep application

- a) The subject will pair the ANNE™ Chest and ANNE™ Limb sensors with the ANNE Sleep mobile application by following the instructions on mobile device
- b) After checking that the sensors are placed correctly and the signal quality is adequate, subjects will then proceed to sleep.

4) Data collection and storage

- a) After a full night of data collection, data will be collected through the ANNE Sleep application. The subject will download the data from the sensor through Bluetooth.
- b) The data will be uploaded automatically to ANNE™ Hub, a secure data repository from the application, and will be associated with the subject ID.
- c) The data will be stored in an EDF data format for further analysis.

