9. SCORING

9.1 ANNE™ Sleep Scoring

The data from ANNE™ will be reviewed and scored for respiratory events by three (3) registered polysomnography technicians (RPSGT) who are blinded to the scoring of the HST, and represent scorers in clinical practice in AASM accredited sleep disorder centers. An average will be taken of the three scores. In order to minimize interscorer variability, the technicians will have >85% concordance. To ensure quality and reproducibility, a board certified sleep medicine physician who is blinded to the experimental condition will review all raw HST data. If AHI determined from ANNE™ Sleep exhibits greater than 15% difference between three RPSGTs, a board-certified sleep medicine physician will provide the final determination of the AHI for ANNE Sleep.

Scoring of ANNE™ Sleep data will follow guidelines established by the American Academy of Sleep Medicine Manual for the Scoring of Sleep and Associated Events (v2.6)⁶. Sleep scoring includes the following variables: total sleep time (TST= the total amount of sleep time scored during the total recording time in minutes). The scoring of respiratory events to evaluate for sleep disordered breathing will also follow AASM scoring rules.

The ANNE™ Sleep will be scored similarly with the system’s onboard sensors as an alternative hypopnea and apnea sensor via PAT. The definition of mild, moderate, or severe obstructive sleep apnea is based on AHI.

- AHI < 5: Normal
- AHI ≥ 5 – <15: Mild
- AHI ≥15 – <30: Moderate
- AHI ≥ 30: Severe

The AHI calculated from ANNE™ Sleep will be considered an estimation of AHI, coined as AHI.

An apnea event is defined as:

STU#: STU00214445

- A drop in peak signal excursion by $\geq 90\%$ of pre-event baseline for ≥ 10 seconds using an oronasal thermal signal, PAP device flow, or an alternative apnea sensor.
- No requirement for a desaturation or an arousal

Hypopnea will be defined by:

- The peak signal excursions drop by $\geq 30\%$ of pre-event baseline using nasal pressure (diagnostic study), PAP device flow (titration study), or an alternative hypopnea sensor (diagnostic study)
- The duration of the $\geq 30\%$ drop in signal excursion is ≥ 10 seconds
- There is a $\geq 4\%$ oxygen desaturation from pre-event baseline and/or the event is associated with an arousal

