10. STATISTICAL ANALYSIS

10.1 Sample size

With a sample size of at least 30, the large amount of within-person data provides high statistical power for all planned analyses, allowing this data set to answer all proposed questions while minimizing study costs and any risk to patients.

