15. DATA MANAGEMENT AND PARTICIPANT CONFIDENTIALITY

Subject identifiable medical information obtained as a result of this study is considered confidential and disclosure to third parties other than the PI and the study team is prohibited. All reports and communications relating to subjects in this study will refer to each subject only by their study identification number. Data generated as a result of this study are available for inspection on request by Food and Drug Administration or other government regulatory agency auditors, Sibel business partners specifically HealthCore, Inc. and the Institutional Review Board (IRB).

Subject identity will be protected through use of a coded list of identifiers which will be maintained separately from the data set. Any paper source documents, questionnaires, and CRFs are kept in a secured area (in a locked cabinet in a locked room) and all electronic data is password protected on a secure NU research server so that only authorized personnel can have access.

STU#: STU00214445

Only authorized research personnel listed on the IRB protocol will have direct access to this data set, although there may be collaborative exchange of de-identified data with other research institutions for assistance in the analysis of raw data.

Data will be capture using NU REDCap, a secure research database. Data stored and used for future research will be de-identified. Data will not be used for future research outside of the scope of this study.

PROTECTED HEALTH INFORMATION (PHI AND HIPAA)

The following PHI will be collected, and is also listed on the consent form for study enrollment:

- Demographic data including name, birthdate, address and phone number
- Results of physical examinations
- Medical history
- Lab tests, or certain health information indicating or relating to a condition as well diaries and questionnaires
- Records about study medication or drugs
- Records about study devices

Entry of any data into a study site clinical record during the duration of the research study is also PHI that may be collected and listed in the consent form. PHI from the above categories may be obtained from the respective study sites and affiliated entities listed as study locations.

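### Technicians are masked to the home sleep test only; no stated masking to subject or night protects the primary outcome of between-night AHI variation

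*Combined protocol and SAP*

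**What the plan says.** **Outcome.** Protocol section 4.1 lists as its first primary outcome: "Analysis of variation between nights of AHI derived from ANNE Sleep system across multiple sleep nights at home". Section 8.1.2 sets the nights: "Subjects will be instructed to set-up both devices on Night One of sleep testing and then only the ANNE device on Nights 2-4". Each completer therefore contributes four ANNE recordings, and only the first has a concurrent home sleep test.

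**Masking.** In section 9.1, three technicians score the ANNE data, and they are people "who are blinded to the scoring of the HST". Their scores are averaged. If their AHI values differ by more than 15%, a sleep physician makes the final determination. The same section also says that "a board certified sleep medicine physician who is blinded to the experimental condition will review all raw HST data". That masking is stated for review of the home-test data. None is stated for the physician who settles the ANNE AHI.

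**Identification of recordings.** Under section 8.1.3, item 4, the uploaded data "will be associated with the subject ID". Section 15 makes this a coded identifier: study reports and communications "will refer to each subject only by their study identification number". Scoring manual section 3.1.1 then tells the scorer: "Select the dataset to score by identifying them through the Patient column". I found no section that hides subject or night from scorers, randomises the order of scoring, or gives one subject's nights to different scorers.

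**The concern.** Masking to the home-test result stops a scorer from steering the ANNE AHI toward the WatchPAT ONE value on night 1. It does nothing for a comparison of ANNE nights with one another, and nights 2–4 have no home-test result to be masked from.

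For the between-night outcome, the information that matters is which recordings come from the same person. If a scorer can see that, there is a natural tendency to treat borderline events consistently from night to night. True night-to-night differences would then be partly scored away, and the reported variation would be too small. Because this is a primary outcome, and one that cannot be repaired later without re-scoring, the plan should close the route rather than rely on its not being taken.

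**Working it through.** The plan gives no figure to reproduce. Section 10.1 says only "With a sample size of at least 30, the large amount of within-person data provides high statistical power for all planned analyses", with no SD, alpha, power value or effect size. The check is therefore a comparison of sections followed by an illustration.

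**1. Can a scorer link nights?** Following the stated workflow, yes, in so far as the same subject ID labels all of a subject's uploads (section 8.1.3) and the scorer picks from a column of patient codes (manual 3.1.1). A coded ID hides the name but not the fact that two recordings share an owner.

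**2. Does labelling leave room for judgement?** Some.
- Manual 3.2 (detecting events) sets numeric limits for chest movement (90% for more than 10 seconds), heart rate (3 bpm within 15 seconds) and SpO2 (3% within 60 seconds). It gives none for attenuation of the PAT signal, which is judged by eye.
- Scorers also decide what is motion artifact, rescale channels by hand (3.1.3), and add or delete events (3.1.4, 3.1.5).

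**3. Would existing safeguards detect it?** No. The three-scorer average and the 15% rule compare scorers within one recording. If all three lean the same way across nights, they still agree with one another. The rule also passes the AHI to a physician with no stated masking for that task. At an AHI of 10, 15% is 1.5 events per hour.

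**4. Illustrative size.** The strength of any pull is my assumption; the documents give no value.

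*Pull toward the subject's mean.* Let x be a night's true AHI and m the subject's four-night mean. The scored value is (1 − λ)x + λm, so its deviation from m is (1 − λ)(x − m). The within-subject SD is multiplied by (1 − λ) and the variance by (1 − λ)².

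| λ | SD factor | Variance factor |
|---|---|---|
| 0.10 | 0.90 | 0.81 |
| 0.20 | 0.80 | 0.64 |
| 0.30 | 0.70 | 0.49 |

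The target matters. The mean of the *other three* nights is (4m − x)/3, which gives an SD factor of 1 − 4λ/3, or 0.87, 0.73 and 0.60 for the same λ.

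*Sequential pull.* Score night 1 as it is, and each later night as (1 − w) times its own AHI plus w times the mean of the earlier scored nights. With independent nights of equal variance, the SD factors are 0.90, 0.80 and 0.71 for w = 0.10, 0.20 and 0.30. This version also needs the order of nights to be visible, which the documents do not show.

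**5. Against sampling error.** With 30 subjects and 4 nights, the within-subject SD has 30 × 3 = 90 degrees of freedom. Its 95% chi-square interval runs from 0.87 to 1.17 times the estimate. Since 1/1.17 = 0.85, a shrinkage of more than about 15% would put the upper limit below the true SD when the estimate sits at its shrunken value.

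**6. Effect on multi-night diagnosis.** Take a subject with mean AHI 12, an assumed within-subject SD of 5 and normal, independent nights. The chance that the four nights fall on both sides of the 15 cut-off is 1 − 0.726⁴ − 0.274⁴ = 0.72. Under the sequential pull, simulation gives 0.61 at w = 0.20 and 0.55 at w = 0.30. For an SD of 3 the sequence is 0.50, 0.38, 0.32; for an SD of 8 it is 0.81, 0.73, 0.66.

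**The case against.** The documents are silent on masking to subject and night; they do not say that scorers are unmasked. The manual is a general Revision A software guide, and its section 3.2 (EnsoSleep) names that platform only as an example. How this study's four nights will be named or listed is not described. This stands, and it is why the point is a gap in the stated procedure and not a demonstrated bias.

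Several features limit the room for linked scoring. Scorers start from automatic pre-labels (manual 3.1.2), apply event-level rules, and do not set total sleep time, which the Hub computes (manual 3.1). This also stands. It narrows the discretion without removing it.

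A reader might infer three stronger things that the documents do not support:

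- *That scorers know which night came first, or see earlier AHI values.* The sample dashboard shows one row per code, no night label, and the same Created stamp on all five rows. The report is generated in the Hub, and no section says that technicians see a previous night's result.
- *That the error favours the device.* Smaller variation would flatter repeatability. But section 2 also lists diagnostic yield from multiple nights as an objective, and step 6 of the working shows that shrinkage would hide changes of category between nights.
- *That a stated intraclass correlation would be inflated.* The plan names no such statistic; section 10.2 plans descriptive summaries of AHI over the nights.

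**Conclusion.** The gap is real and worth closing. A primary outcome depends on comparing nights within a subject, the stated masking does not cover that comparison, and the stated workflow lets a scorer identify recordings by subject. Linked scoring could understate between-night variation, and the three-scorer average and 15% rule would not reveal it if it were shared.

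Whether it would occur, and how large it would be, cannot be found from the documents. The 10–30% reduction in within-subject SD rests wholly on an assumed pull of 10–30% toward the subject's mean. If the pull is near zero, there is no effect. The net consequence could be overstated repeatability or an understated gain from extra nights. No sample size or power figure changes.

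**What to change.** Add to protocol section 9.1 and to the scoring manual, before scoring begins:

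- Each night's EDF file is presented to the technicians, and to the physician who adjudicates the ANNE AHI, under a random recording code with no subject ID, night number or date.
- Recordings are scored in random order across subjects and nights.
- The key is held by someone not involved in scoring until scoring is locked.

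If scorers are already masked this way in practice, stating it in section 9.1 is enough.

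This is a cheap improvement. It needs no extra subjects or nights. The cost is recoding at least 30 × 4 = 120 files, and more if early leavers contribute, since section 12 keeps their data unless they ask otherwise in writing. Because upload is automatic under the subject ID and scored files go back to the Hub for reporting, that link has to be broken and rebuilt. Random order also means scoring in batches and not as recordings arrive.
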